7. RATIONALE AND BACKGROUND

Myasthenia gravis (MG) is an autoimmune disease caused by immunoglobulin G (IgG) antibodies against postsynaptic antigens at the neuromuscular junction. IgG autoantibodies impair neuromuscular transmission by binding to acetylcholine receptors (AChR), muscle-specific tyrosine kinase (MuSK) or low-density lipoprotein receptor-related protein 4 (LRP4).

From an immunological point of view, approximately 80% of patients with MG have detectable antibodies against AChR. These patients are known as AChR antibody positive.

The estimated prevalence rate for MG is 77.7 per million persons (range 15–179) and the estimated incidence rate is 5.3 per million person-years (range 1.7–21.3) [Carr 2010].

MG occurs in both genders, at all ages, and in all races [Carr 2010, McGrogan 2010]. The most common age of MG onset is between 20 and 40 years. In this age group, about 60% of patients are women. In older age groups, men are affected more often, and the disease is often misdiagnosed. As a result, there is a bimodal distribution with a female predominance in the second to third decade of life and male predominance in the sixth to eighth decade [Philips 2004, Spillane 2012].

MG can be classified into various subgroups based upon antibody status, age of onset and/or degree of muscle involvement. Ocular symptoms are the most common initial presentation of disease and about two thirds of ocular MG patients progress to generalised MG (gMG) within the first 2-3 years (Anil 2020).

A considerable variation exists in the management of gMG, and treatment is not standardized. Current treatment options include acetylcholinesterase (AChE) inhibitors, and long-term immune therapies with immunosuppressive agents such as corticosteroids, azathioprine, cyclosporine, and mycophenolate, but tacrolimus, methotrexate, and cyclophosphamide are also used. There is no consensus on the choice of immunosuppressive agent. Thymectomy is also a treatment option for patients with generalised MG. Monoclonal antibodies such as eculizumab or rituximab are used for more refractory cases [Vyvgart EPAR].

Short term immune therapies such as plasmapheresis/plasma exchange (PLEX) and intravenous immunoglobulins (IVIg) are typically used for treatment of severe exacerbations of gMG [Vyvgart EPAR].

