Malignancy	Any adverse event (AE) within the Standardised MedDRA Query (SMQ) Malignancies (Narrow) .	Proportion of patients who report events of malignancy during the course of the study in the efgartigimod treated cohort compared to the non-efgartigimod cohort. Incidence rate of events of malignancy per patient-years exposed in the efgartigimod treated cohort compared to the non-efgartigimod cohort.
Adverse event (AE)	Any untoward medical occurrence in a patient administered a pharmaceutical product or device and that does not necessarily have a causal relationship between the product and the event. An AE can, therefore, be any unfavorable or unintended sign (including an abnormal laboratory finding) or symptom temporally associated with a medicinal product, whether or not related to the medicinal product.	Proportion of patients who report AEs during the course of the study in the efgartigimod treated cohort compared to the non-efgartigimod cohort. Incidence rate of AEs per patient-years exposed in the efgartigimod treated cohort compared to the non-efgartigimod cohort.
Serious adverse event (SAE)	As per definition in Section 11.	Proportion of patients who report SAEs during the course of the study in the efgartigimod treated cohort compared to the non-efgartigimod cohort. Incidence rate of SAEs per patient-years exposed in the efgartigimod treated cohort compared to the non-efgartigimod cohort.

AEs (serious and non-serious) in immunocompromised patients
	
Immunocompromised definition (moderate or severe) based upon Centre for Disease Prevention (CDC) People Who Are Immunocompromised CDC.
	
Proportion of AEs/SAEs reported in immunocompromised patients and immunocompetent patients in the efgartigimod cohort.
 
Incidence rate of AEs/SAEs per patient-years exposed in immunocompromised patients and immunocompetent patients in the efgartigimod cohort.

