The study design includes an efgartigimod cohort and a comparator cohort of non-efgartigimod treated patients. The duration of the study is a maximum of 10 years (5 years of enrolment and 5 years of follow up). Over this time period, standard of care for the treatment of gMG is likely to evolve with the introduction of new medicinal products such as ultomiris (recently approved) and rozanolixizumab and zilucoplan (currently under review with an approval expected by end of 2023) and the potential for patients to switch treatments during this time. The comparator group, and indeed the efgartigimod group, will therefore be heterogenous in terms of treatments, thus limiting the interpretability of the results.

Furthermore, in countries where efgartigimod is marketed, it is likely that the efgartigimod cohort and the comparator cohort will differ in terms of disease severity with the more severe patients receiving efgartigimod. Thus, there will be an inherent selection bias. This could be solved by recruiting the comparator patients from countries where efgartigimod is not marketed. However, this will introduce further biases in terms of differing standards of care.

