11.1 Definitions

AE: Any untoward medical occurrence in a patient administered a pharmaceutical product or device and that does not necessarily have a causal relationship between the product and the event. An AE can, therefore, be any unfavorable or unintended sign (including an abnormal laboratory finding) or symptom temporally associated with a medicinal product, whether or not related to the medicinal product.

SAE: Any untoward medical occurrence which:

- Results in death.
- Is life-threatening: The term life threatening in the definition of serious refers to an event in which the participant was at risk of death at the time of the event. It does not refer to an event, which hypothetically might have caused death, if it were more severe.
- Requires inpatient hospitalization or prolongs hospitalization: In general, hospitalization signifies that the participant has been admitted at the hospital or emergency ward for observation and/or treatment that would not have been appropriate in the physician's office or outpatient setting. Complications that occur during hospitalization are AEs. If a complication prolongs hospitalization or fulfills any other seriousness criteria, the event will be considered serious. When in doubt as to whether hospitalization occurred or was necessary, the AE is considered serious. Hospitalization for elective treatment of a pre-existing condition that did not worsen from screening will not be collected as an AE.
- Results in persistent or permanent disability or incapacitation: The term disability means a substantial disruption of a person's ability to conduct normal life functions. This definition is not intended to include events of relatively minor medical significance such as uncomplicated headache, nausea, vomiting, diarrhea, influenza, and accidental trauma (e.g., sprained ankle) that can interfere with or prevent everyday life functions but do not constitute a substantial disruption.

- Results in a congenital anomaly or birth defect.
- Other situations: Any important medical event that may not be immediately life-threatening or result in death or hospitalization but, based upon appropriate medical judgment, may jeopardize the patient or may require medical or surgical intervention to prevent one of the other outcomes listed in the definition above, should also be reported as an SAE.

Special situations:

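### The all-AE and all-SAE cohort comparisons include worsening of gMG itself, so drug benefit or residual channelling could mask or mimic a difference in other events

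*Protocol*

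**What the plan says.** Section 8 makes overall long-term safety, including serious infections, the primary objective. Table 2 in Section 9.3 then lists the events compared between cohorts. Two are totals: all AEs and all SAEs, each as a proportion of patients and as a rate. The SAE row reads "Proportion of patients who report SAEs during the course of the study in the efgartigimod treated cohort compared to the non-efgartigimod cohort".

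Section 11.1 defines these totals broadly:
- The AE definition begins "AE: Any untoward medical occurrence in a patient administered a pharmaceutical product or device and that does not necessarily have a causal relationship" and extends to any sign or "symptom temporally associated with a medicinal product, whether or not related to the medicinal product".
- An SAE is "Any untoward medical occurrence which" meets a seriousness criterion. One criterion begins "Requires inpatient hospitalization or prolongs hospitalization: In general, hospitalization signifies that the participant has been admitted at the hospital or emergency ward".
- The only carve-out for an existing condition is "Hospitalization for elective treatment of a pre-existing condition that did not worsen from screening will not be collected as an AE".

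Section 9.7 gives the other events of interest the same methods as serious infection: logistic regression on patients with and without an event, and Cox regression on time to first event. Treatment and country are the base covariates.

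Table 1 records myasthenic crises only as previous history, at baseline. Section 9.9 expects cohorts of unequal severity in countries where the drug is marketed, with "the more severe patients receiving efgartigimod".

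**The concern.** Efgartigimod is a treatment for gMG, so the disease it treats also contributes to the safety totals. Exacerbations can be serious: Section 7 says that plasma exchange and IVIg "are typically used for treatment of severe exacerbations of gMG". If the drug works, its cohort should have fewer such events. If sicker patients receive it and adjustment is incomplete, its cohort should have more. Neither shift measures harm, yet both move the all-AE and all-SAE contrasts.

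The risk is in interpretation. A flat SAE total could conceal a rise in SAEs unrelated to MG, and a raised total could reflect disease severity alone.

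**Working it through.** **1. Is MG worsening in the totals?** The protocol never says so in words, so it has to be inferred. The AE and SAE definitions have no exclusion for the treated disease. The one carve-out covers elective admission for a condition that has not worsened, so an unplanned admission for worsened gMG stays in. Section 11.1 lists lack of efficacy as a special situation, but nothing says that such events leave the AE and SAE counts. MG worsening is therefore counted.

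**2. Can the reader separate it afterwards?** Section 9.7 presents AEs by SOC and preferred term, so MG terms will be visible by cohort. Those tables give counts per term. A patient can have several terms, so the proportion with at least one non-MG SAE cannot be rebuilt from them. Nor can the time to the first non-MG SAE: in the Cox model, a patient whose first SAE is a crisis contributes that date, and a later non-MG SAE never enters.

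**3. Size on the rate scale (assumed inputs).** Let s be the share of comparator SAEs that are MG worsening. Then

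total RR = s × RR_MG + (1 − s) × RR_other.

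- Masking, RR_MG = 0.6 (a 40% fall): the RR_other that gives a total of 1.0 is (1 − 0.6s)/(1 − s). For s = 0.3 this is 0.82/0.70 = 1.17. For s = 0.5 it is 0.70/0.50 = 1.40.
- Mimicry, RR_MG = 1.5 and RR_other = 1: for s = 0.3, 0.45 + 0.70 = 1.15. For s = 0.5, 0.75 + 0.50 = 1.25.

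**4. Size on the patient-proportion scale (assumed inputs).** The plan's own figure first: 270 per arm, 20% against 31%, two-sided 0.05, stated power 84% (Section 9.5). The normal approximation gives 83.7% with pooled variance and 84.0% unpooled, so the figure reproduces. It was set for serious infection and is not in dispute; it is borrowed here only as a yardstick for non-MG SAEs.

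Assuming independence, risk of any SAE = 1 − (1 − p_other)(1 − p_MG). For MG risks of 20% against 10%: comparator 1 − 0.80 × 0.80 = 36.0%; efgartigimod 1 − 0.69 × 0.90 = 37.9%.

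| True non-MG SAE risk | Assumed MG SAE risk (comparator, efgartigimod) | Pooled risk | Difference (points) | Chance of significance, 270 per arm |
|---|---|---|---|---|
| 20%, 31% | none | 20.0%, 31.0% | +11.0 | 84% |
| 20%, 31% | 10%, 10% | 28.0%, 37.9% | +9.9 | 69% |
| 20%, 31% | 10%, 5% | 28.0%, 34.45% | +6.45 | 37% |
| 20%, 31% | 20%, 10% | 36.0%, 37.9% | +1.9 | about 7% |
| 20%, 31% | 30%, 15% | 44.0%, 41.35% | −2.65 | sign reversed |
| 20%, 20% | 10%, 15% | 28.0%, 32.0% | +4.0 | 17% |
| 20%, 20% | 10%, 20% | 28.0%, 36.0% | +8.0 | 51% |
| 20%, 20% | 10%, 25% | 28.0%, 40.0% | +12.0 | 84% |

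The last three rows have no true harm and no adjustment for severity.

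**The case against.** The strongest reply has four parts.

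- **This is detail for the SAP.** A term grouping and a repeat table commonly belong there, Section 9.7 defers details to it, and the SAP is not shown. It may already contain the split. That stands as a limit on the point. But Table 2 itself fixes the list of events and the pooled comparison, and MG worsening is not on that list.
- **MG events are already visible.** The SOC and preferred-term tables show them, and MG-ADL, MGFA class and acute plasma exchange or IVIg are collected in follow-up. A reader might infer that nothing separates MG events; the documents do not support that. What the tables lack is a modelled or patient-level comparison without MG terms.
- **Channelling is addressed.** Section 9.1 matches on MG-ADL band, age and region. Section 9.7 adds covariates or a propensity score for imbalanced baseline measures, and Section 9.9 admits the limitation. This stands for the channelling part. Baseline adjustment cannot remove an on-treatment reduction in MG events.
- **The consequence is limited.** A reader might infer that the answer to the primary objective would be wrong either way. The documents do not support this. Serious infection is defined by its SOC and malignancy by an SMQ, so neither counts MG worsening. The AE and SAE totals are two rows among several, and Section 9.5 calls the analysis descriptive and exploratory.

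A reader might also infer that the safety statement should rest only on events without MG worsening. That is debatable. If treatment or its interruption worsened MG, such a headline would hide it.

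**Conclusion.** The point holds for the all-AE and all-SAE comparisons in Table 2 and the models applied to them. These totals include gMG worsening, and drug benefit or residual channelling could mask or mimic a difference in other events. The Cox model can also lose a non-MG SAE that follows an MG event.

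The size is unknown. The protocol gives no rate of MG-worsening SAEs, so the 1.17- to 1.40-fold figure rests on an assumed 30-50% share and an assumed 40% reduction. The table of proportions rests on further assumed risks and on independence. These figures show that the mechanism can matter; they do not predict its size. This is a worthwhile, low-cost improvement to a comparison that the protocol fixes, and it leaves the sample size and the serious-infection and malignancy analyses untouched.

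**What to change.** Before the first cohort comparison:

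1. Fix a MedDRA preferred-term list for MG worsening and crisis.
2. Add it to Table 2 as its own event of interest, compared between cohorts.
3. Report the all-AE and all-SAE proportions, rates, logistic models and Cox models both with and without these terms. Interpret the two side by side and keep the current total.

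The cost is one term list and a second version of the AE and SAE tables and models, from data that will already be coded. No new data, visits or patients are needed. Fixing the list early avoids a choice made after seeing the results. Excluding MG terms does not remove severity confounding of the remaining events, so the matching and adjustment in Sections 9.1 and 9.7 are still needed for both versions.

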8. RESEARCH QUESTION AND OBJECTIVES

A non-interventional Post-Authorization Safety Study (PASS) in a post-marketing setting comparing cohorts of patients with gMG treated with efgartigimod to those treated with other MG medication for 10 years, in order to estimate incidence rates of serious infection and other safety events.

Primary Objective

- To evaluate the overall long-term safety of efgartigimod including the occurrence of serious infections in gMG patients treated with efgartigimod compared to gMG patients not exposed to efgartigimod.

Exploratory Objectives

- To evaluate the safety of efgartigimod in immunocompromised patients
- To evaluate the safety of efgartigimod administered to patients treated with monoclonal antibodies
- To evaluate the safety of efgartigimod in patients receiving live/attenuated vaccine
- To evaluate the safety of efgartigimod in patients with moderate to severe renal impairment

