9.3 Variables

Electronic case report forms (eCRFs) will be specifically designed for the collection of data from this study. An overview of the categories of study variables (raw data) to be collected for each enrolled patient is summarized in [Table 1](#). There may be some missing data if any assessments are not performed as part of normal clinical practice.

Table 1: Study Variables*

Category	Variables	Baseline	Follow up
Confirmation of eligibility, demographics, study status	
 Date of appropriate informed consent for study enrolment Eligibility assessment Demographic characteristics 	✓	
Past and current medical history	
 Relevant medical history including key co-morbidities (including past history of infections) 	✓	

Category	Variables	Baseline	Follow up
	
 Immune status (immunocompromised or immunocompetent) 	✓	✓
gMG Disease	
 Date of diagnosis 	✓	
	
 Criteria used for diagnosis of gMG 	✓	
	
 Antibody status (AChR, MuSK, anti-LRP4)/date 	✓	
	
 Clinical classification (Myasthenia Gravis Foundation of America recommendations) (Jaretzki, 2000) 	✓	✓
	
 Previous myasthenia crises 	✓	
	
 Thymectomy 
 Date Histology 	✓	✓
	
 MG-ADL questionnaire 	✓	✓
Renal function	
 Estimated glomerular filtration rate (eGFR) 	✓ (Most recent prior to initiation of efgartigimod therapy)	✓
gMG treatments in period from diagnosis prior to enrollment (excluding efgartigimod)	
 Drug name, start and stop dates 
 Acetylcholinesterase inhibitors Corticosteroids Other immunosuppressants (specify) Monoclonal antibodies (specify) Plasmapheresis/plasma exchange acute Plasmapheresis/plasma exchange chronic IVIg therapy acute IVIg therapy chronic Other 	✓	

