
AEs (serious and non-serious) in patients treated with monoclonal antibodies
	
Patients receiving monoclonal antibodies other than FcRn (e.g., adalimumab, tocilizumab, ixekizumab, rituximab) within 6 months prior to efgartigimod administration.
	
Proportion of AEs/SAEs reported in patients treated with monoclonal antibodies vs patients not treated with monoclonal antibodies in the efgartigimod cohort.
 
Incidence rate of AEs/SAEs per patient-years exposed in patients treated with monoclonal antibodies vs patients not treated with monoclonal antibodies in the efgartigimod cohort.

AEs (serious and non-serious) in patients treated with live attenuated vaccine
	
Patients receiving live/attenuated vaccine (e.g., live-attenuated flu vaccine, measles, mumps and rubella, polio, smallpox, chickenpox, yellow fever, Japanese encephalitis, shingles, rotavirus) in the period of 4 weeks prior to or 2 weeks after efgartigimod administration.
	
Proportion of AEs/SAEs reported in patients who have received live/attenuated vaccine vs patients who have not received live/attenuated vaccine in the efgartigimod cohort.
 
Incidence rate of AEs/SAEs per patient-years exposed in patients who have received live/attenuated vaccine vs patients who have not received live/attenuated vaccine in the efgartigimod cohort.

AEs (serious and non-serious) in patients with moderate to severe renal impairment
	
Moderate renal impairment: eGFR 30-59 mL/min/1.73 m² Severe renal impairment: eGFR < 30 mL/min/1.73 m²
	
Proportion of AEs/SAEs reported in patients with moderate renal impairment vs patients who have normal renal function in the efgartigimod cohort.
 
Incidence rate of AEs/SAEs per patient-years exposed in patients with moderate renal impairment vs patients who have normal renal function in the efgartigimod cohort.
 
Proportion of AEs/SAEs reported in patients with severe renal impairment vs patients who have normal renal function in the efgartigimod cohort.

		Incidence rate of AEs/SAEs per patient-years exposed in patients with severe renal impairment vs patients who have normal renal function in the efgartigimod cohort.
--	--	--

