Balance of the baseline measures, including age, MG-ADL score and region matched at enrollment and other demographic and disease characteristics, will be assessed. The imbalanced measures which are considered to be potential confounders based on clinical judgement will be added to the above base models as covariates. If a large number of imbalanced potential confounders are identified after the enrollment is complete, a propensity score method will be applied instead. More details will be given in the SAP.

Subgroup analyses will be performed using descriptive statistics on the subset of patients who remained on efgartigimod throughout the duration of the PASS. In addition, subgroup analyses of treatment cycle per year or administration per year (four administrations in one cycle if not interrupted), subgroup analyses of time since the last administration of efgartigimod prior to the event occurrence in intervals of every 4 weeks will be performed, and subgroup analysis of patients using efgartigimod as add-on or single treatment will be performed if sample size allows. Since one patient may have multiple same events with different time to the last administration, one patient may be assigned to multiple time intervals.

Events of Interest

Statistical analysis of malignancy and other events of interest will follow the same method as those for serious infections

Exploratory objectives

Descriptive statistics will be used to summarise the long-term safety of efgartigimod for specific subgroups. The number and percentage of patients with AEs/SAEs will be presented. The rate per person-year exposure with a 95% CI will be constructed using asymptomatic normal approximation. This will be done for the following subgroups:

- immunocompromised patients and immunocompetent patients.
- patients treated with monoclonal antibodies and patients not treated with monoclonal antibodies.
- patients who have received live/attenuated vaccine and patients who have not received live/attenuated vaccine.
- patients with moderate to severe renal impairment and patients with normal renal function or mild renal impairment.

Missing values

No imputation will be applied to occurrence of serious infection, malignancy or other safety events.

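### Table 2 gives three exploratory subgroups no same-condition comparator, so the planned contrast cannot separate background risk from risk added by efgartigimod

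*Protocol*

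**What the plan says.** Section 8 of the protocol sets four exploratory objectives, the first being "To evaluate the safety of efgartigimod in immunocompromised patients". Section 7 explains that the EU Risk Management Plan lists these populations as missing information.

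Table 2 in Section 9.3 then fixes the measures:
- Immune status: "Proportion of AEs/SAEs reported in immunocompromised patients and immunocompetent patients in the efgartigimod cohort".
- Antibodies: "Proportion of AEs/SAEs reported in patients treated with monoclonal antibodies vs patients not treated with monoclonal antibodies in the efgartigimod cohort".
- Renal function: "Proportion of AEs/SAEs reported in patients with moderate renal impairment vs patients who have normal renal function in the efgartigimod cohort", with a parallel entry for severe impairment.

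Each has a matching incidence-rate measure with the same restriction to the efgartigimod cohort. For serious infection, malignancy, AEs and SAEs the same table compares cohorts instead, for example "Incidence rate of SAEs per patient-years exposed in the efgartigimod treated cohort compared to the non-efgartigimod cohort".

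Section 9.7 says of the exploratory objectives: "Descriptive statistics will be used to summarise the long-term safety of efgartigimod for specific subgroups". It lists pairs such as "immunocompromised patients and immunocompetent patients". It does not repeat the cohort restriction, but it names no comparison with non-efgartigimod patients who have the same condition.

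**The concern.** The objectives ask how safe efgartigimod is in patients who are immunocompromised, have renal impairment or receive other antibodies. Every patient in the planned contrast belongs to the efgartigimod cohort, and the groups differ by the condition. Such conditions can carry their own excess of infections and other events. A raised rate could therefore be background, an extra effect of efgartigimod in that group, or both.

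Two misreadings are possible: an excess due only to the condition is reported as a signal, or a real added risk is put down to the condition. The study plans 340 unexposed gMG patients, and Table 1 lists immune status, eGFR and gMG antibody treatment for both cohorts. A same-condition reference is thus largely within reach, but Table 2 does not ask for it.

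**Working it through.** **The plan's own figures.** The protocol gives no figure for these subgroup contrasts. Its whole-cohort figures in Section 9.5 reproduce. For 20% vs 31% with 270 per arm, the unpooled standard error is √[(0.2×0.8 + 0.31×0.69)/270] = 0.0372, and 0.11/0.0372 − 1.96 ≈ 1.00, so power is 84% (stated: 84%). For drop-out, 270/0.80 = 337.5, or 338 (stated: 340). Neither figure bears on the point.

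**What the planned ratio estimates.** Let p0 and p1 be the risks without efgartigimod when the condition is absent and present, and d0 and d1 the risk ratios for efgartigimod in those groups.
- Within the efgartigimod cohort: W = (p1·d1)/(p0·d0) = (p1/p0) × (d1/d0).
- Across cohorts, condition present: C = (p1·d1)/p1 = d1, if there is no confounding.

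**Illustration.** All risks and effects below are assumed; the protocol gives none by subgroup.

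| Situation | p0 | p1 | d0 | d1 | Efgartigimod risk, absent / present | W | C |
|---|---|---|---|---|---|---|---|
| A. No efgartigimod effect | 20% | 40% | 1 | 1 | 20% / 40% | 2.0 | 1.0 |
| B. Effect in both groups | 20% | 40% | 1.5 | 1.5 | 30% / 60% | 2.0 | 1.5 |
| C. Effect only with the condition | 20% | 40% | 1 | 1.5 | 20% / 60% | 3.0 | 1.5 |
| D. No effect, stronger condition | 20% | 60% | 1 | 1 | 20% / 60% | 3.0 | 1.0 |

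A and B share the same W. C and D share the same W and also the same absolute risks in the efgartigimod cohort, so reporting subgroup rates there does not tell them apart either. The same-condition comparison does, in both pairs. If the condition raises risk 1.5-fold instead of 2-fold, W is 1.5 with no drug effect and 2.25 with a 1.5-fold effect confined to the condition; C is again 1.0 and 1.5. The level of p0 cancels.

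**Precision of the added comparison.** Assume 270 per cohort, 30% risk in both cohorts, and an equal subgroup share in each. The 95% half-width of the difference is 1.96 × √(2×0.3×0.7/n).

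| Subgroup share | n per cohort | Half-width (points) |
|---|---|---|
| 10% | 27 | 24.4 |
| 20% | 54 | 17.3 |
| 30% | 81 | 14.1 |
| 50% | 135 | 10.9 |

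At a 20% share the planned within-cohort contrast (54 vs 216) has half-width 1.96 × √[0.21 × (1/54 + 1/216)] = 13.7 points. The added comparison is less precise, but not of a different order.

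**The case against.** **A reader might infer that the planned contrast shows only the risk of the condition.** It does not. W also carries d1/d0, so an effect confined to the subgroup does move it (from 2.0 in A to 3.0 in C). Such an excess would be visible; what is missing is the means to attribute it.

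**An effect common to all patients is examined elsewhere.** Table 2 compares the main events between cohorts, and Section 9.7 adds logistic and Cox models, so situation B would not go unexamined. This stands, and it narrows the point. An effect confined to the subgroup, however, is diluted in the overall comparison. In situation C with a 20% share, the overall risks are 0.8×20% + 0.2×60% = 28% and 0.8×20% + 0.2×40% = 24%, a ratio of 1.17 instead of 1.5.

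**A reader might also infer that the protocol contradicts itself.** It does not. Only the primary objective in Section 8 names unexposed patients as comparator; the exploratory objectives name none, and describing safety in unstudied groups is a legitimate aim.

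**Section 9.7 is broader than Table 2.** The Safety Population covers both cohorts, and other events of interest are to follow the serious-infection method. The SAP could therefore tabulate the comparator. But the paragraph on exploratory objectives gives only present/absent pairs, and Table 2 is explicit about the cohort.

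**The added comparison has its own weaknesses.** Section 9.9 expects more severe patients to receive efgartigimod, and matching covers only age, MG-ADL and region. With small cells as well, this argues against making it the main reference, though not against reporting it. Table 1 data are also collected only where routine practice provides them.

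**Conclusion.** The point holds as a limitation of the exploratory analyses for immune status, renal function and antibody treatment. Table 2 fixes a contrast that mixes background risk with effect modification and supplies no same-condition reference, so by itself it cannot show whether efgartigimod adds risk in these patients. That reading rests on the text alone.

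The size depends on assumptions. With a condition that raises risk 1.5- to 2-fold, the planned ratio would be 1.5 to 2.0 with no efgartigimod effect at all. The values of 1.0 and 1.5 for the cross-cohort ratio assume no confounding, which Section 9.9 gives reason to doubt. The primary comparison and its sample size are unaffected.

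**What to change.** In Table 2 and Section 9.7, for the immune-status, renal and antibody subgroups, add the proportion and incidence rate with 95% CI in the same subgroup of the non-efgartigimod cohort, and the cross-cohort difference or ratio. Report these alongside the within-cohort contrast. Label them descriptive, citing small cells and the channelling described in Section 9.9.

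Three definitions are needed:
- **Baseline eGFR.** Table 1 ties it to the start of efgartigimod. For comparators, use the most recent value before enrolment.
- **Antibody window.** Table 2 ties the 6 months to efgartigimod administration. For comparators, count back from enrolment.
- **Antibody scope.** Limit the cross-cohort comparison to gMG monoclonal antibodies. Pre-enrolment dates are collected only for gMG treatments; other comedications are recorded from enrolment onwards.

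Leave live vaccines out of the cross-cohort comparison, because their collection window ends relative to the last efgartigimod dose. Also reconcile the renal reference group: Table 2 uses normal function, while Section 9.7 uses normal function or mild impairment.

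The cost is extra table columns and a few lines of definition. No new variables are needed. The price is modest precision, so the added estimates inform interpretation and do not support a test.
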